1. STUDY SYNOPSIS

Protocol Number

CCN_CT02

Protocol Title

Phase I/IIa Dose Escalation Safety and Efficacy Study of Human Embryonic Stem Cell-Derived Retinal Pigment Epithelium Cells Transplanted Subretinally in Patients with Advanced Dry-Form Age-Related Macular Degeneration (Geographic Atrophy)

Sponsor

Cell Cure Neurosciences Ltd./BioTime, Inc.

Study Centers and Planned Geographical Distribution

Multicenter multinational trial

Clinical Phase

Phase I/IIa study

Investigational Product

OpRegen® is a cell-based product composed of retinal pigment epithelium (RPE) cells, derived from human embryonic stem cells (hESCs) through a process of directed differentiation. OpRegen® can be implanted as a single cell suspension to form a targeted suspension of 50×10^3 to 200×10^3 in a total volume of 50-100 μL in either an ophthalmic

Study Duration

- Screening period of up to [REDACTED].
- Part 1: Eligible subjects will be enrolled into Part 1 of the trial for approximately 52 weeks (up to ± 14 days) for a post-implantation follow up assessment.
- Part 2: Following the successful completion of Part 1 of the study, subjects will continue into Part 2 defined as the long term follow up with evaluations at [REDACTED], [REDACTED].

Study Objectives

Primary Objectives

To evaluate the safety and tolerability of human embryonic stem cell-derived retinal pigment epithelium cells (OpRegen®), transplanted subretinally to subjects with advanced dry age-related macular degeneration (AMD) with geographic atrophy (GA).

Secondary Objectives

To evaluate the preliminary efficacy of OpRegen® treatment by assessing the changes in ophthalmological parameters as measured by various methods of primary clinical relevance.

¹ Refer to Section 2.3 in the Investigator Brochure for more information about the Product Description

[REDACTED]

Study Endpoints

Safety and Tolerability Endpoints

Safety and tolerability of OpRegen® treatment will be assessed by:

- Incidence and frequency of treatment emergent adverse events (AEs)
- Treatment emergent changes in the following variables:
 - Vital signs
 - Hematology/ Blood Chemistry/ Urinalysis
 - Physical examination
 - Ophthalmological evaluations including:
 - ✓ Best Corrected Visual Acuity (BCVA)
 - ✓ Dilated Fundus Exam
 - ✓ Intraocular Pressure (IOP)
 - ✓ Slit Lamp Examination (SLE)
 - ✓ Spectral Domain Optical Coherence Tomography (SD-OCT)
 - ✓ Fluorescein Angiography (FA)
 - ✓ Microperimetry
 - ✓ Fundus Autofluorescence (FAF)

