15. POST-STUDY LONG TERM FOLLOW-UP

Long-term follow-up will occur for up to [REDACTED]

During the long-term follow up the subjects will undergo routine testing including vital signs and general physical examination and clinical eye examination including IOP, slit lamp and dilated fundus examination. An optional malignant hematological transformation test and immunosuppression assessment may be performed at the [REDACTED] [REDACTED] to follow-up for potential adverse reactions associated with immunosuppression therapy. Routine laboratory tests will be performed at each visit, including blood count, chemistry (serum electrolytes), urinalysis, and rheumatology (including ESR and CRP). Also, functional eye testing will be performed, as described in Section 10.3. All AEs and concomitant medications should be reported over the course of the long-term follow-up period. [Table 3](#) summarizes the evaluations that will be performed during the long-term follow up.

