21.1.5 Event Expectation

Unexpected: An event is considered “unexpected” when its nature (specificity) or severity is not consistent with the list of potential adverse reactions included in the current Investigator’s brochure.

Expected: An event is considered “expected” when its nature and severity are consistent with the list of potential adverse reactions included in the current IB.

21.1.6 **Recording of Adverse Events**

At each contact with the subject the study Investigator or his/her designee will seek information on AEs by specific questioning and examination. Information on all AEs will be immediately recorded in the source document and the data will be transferred to the CRF. All clearly related signs, symptoms and abnormal results will be recorded in the source document. The CRF will include a description, onset and resolution date, duration, maximum severity, assessment of causality, other suspected agent, subject's preexisting disease, action taken and outcome.

All AEs occurring during the study and long-term follow up period will be recorded and graded as described in [Section 21.1.7](#). The clinical course of each event will be followed until resolution, stabilization or until it has been reported as non-related to the investigational product.

21.1.7 **Toxicity Grading**

The AEs will be graded using NCI's CTCAE.

The list of potential ocular toxicities and their grading is shown in [Table 6](#). This list is a modification of the Ocular/Visual Adverse events v.3.0 (CTCAE), considering the specific subject population and the circumstances of the intervention.

The following AEs are defined as ocular toxicity and are to be assessed for grading as follows:

Table 6. Ocular toxicity scale

Toxicity	Grade 1	Grade 2	Grade 3 SAE	Grade 4 SAE
Keratitis (corneal inflammation/cornea ulceration)	Abnormal ophthalmologic changes only; intervention not indicated	Symptomatic; Medical intervention indicated	Symptomatic; Surgical intervention indicated	Perforation or blindness (worse than baseline visual function)
Glaucoma	Elevated intraocular pressure (EIOP) warranting topical agent for intervention	EIOP requiring topical agents and oral agents for intervention	EIOP requires operative intervention	Uncontrolled EIOP, resulting in blindness (worse than baseline visual function)

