22.2 ANALYSIS SETS

22.2.1 Modified Intent-to-Treat (mITT) Analysis Set

The Modified Intent-to-Treat (mITT) analysis set will consist of all subjects who have been enrolled to the trial and received the OpRegen® implantation. This analysis set, which will include all data captured in database for these subjects, will serve as the primary Analysis Set for inference.

22.2.2 **Per Protocol (PP) Analysis Set**

The Per Protocol (PP) analysis set is a subset of the mITT Analysis Set and will consist of all subjects who have been enrolled into the trial, received the OpRegen® implantation and violated none of the major protocol guidelines.

22.3 **SIGNIFICANCE LEVEL**

No formal hypothesis testing is planned for this study. However, a significance level of 0.05 using two-tailed tests will be utilized in the case that exploratory significance testing will be performed.

22.4 **INTERIM REPORTS**

Comprehensive interim reports of accumulated safety, tolerability and preliminary available efficacy data will be presented to the independent Data Safety Monitoring Board (DSMB).

Depending on the safety data available, there will be a DSMB recommendation to pursue one of the following alternatives: proceed to the next higher dose; stop dose escalation; investigate a lower dose; or repeat a dose level.

22.5 **DESCRIPTIVE STATISTICS**

All measured variables and derived parameters will be listed individually and if appropriate, presented in summary tables by dose regimen group and overall, providing sample size, absolute and relative frequency for categorical variables, or sample size, arithmetic mean, standard deviation, median, minimum and maximum for continuous variables. Confidence intervals will be presented for the efficacy endpoints for exploratory purposes only.

22.6 **MISSING DATA**

Every effort will be made to complete follow-up for all subjects and avoid missing data, in particular regarding essential items. For other cases of missing data, the “last observed value” (LOV) approach will be used when appropriate.

22.7 **SUBJECT DISPOSITION**

Data from subjects who are screened but not treated, subjects in the mITT and PP Analysis Sets, as well as trial withdrawals from study follow-up will be summarized using descriptive statistics.

22.8 **DEMOGRAPHIC AND BASELINE CHARACTERISTICS**

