**Figure 1. Protocol Enrollment Schema**

## 4.1 Definitions

### 4.1.1 Study Day and Study Reference Period

Time will be measured as Study Day defined according to Clinical Data Interchange Standards Consortium (CDISC) standard. That is, the date of the OpRegen injection is [REDACTED]. The date before the OpRegen injection is [REDACTED]. Study day can be calculated as follows:

Study Day = visit date – date of OpRegen injection

Last study day for a subject is the subject’s last clinical visit date recorded on the subject status [eCRF](#). If this date is missing for a subject, the last date found in the clinical database (e.g., clinical lab test date or date of vital sign collection) will be used as the last study date for the subject.

Total days on study are the total number of days a subject has been followed up after OpRegen injection. Mathematically it can be calculated as follows:

Total days on study = last study date – date of OpRegen injection + 1

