### 7.1.6 Adverse Events

The collection period for adverse events for the purposes of this protocol begins once the subject has signed the informed consent form and ends after the [REDACTED]. All adverse events will be listed by subject. The [MedDRA](#) (Version 25.0) will be used to classify all adverse events by SOC and PT.

A treatment emergent adverse event ([TEAE](#)) will be considered as any [AE](#) that starts on or after the date and time of the OpRegen administration, or if an [AE](#) that started before the OpRegen injection worsened after the administration of the investigational product.

A topline summary of treatment emergent adverse events with the number of events, number of subjects, and percentage of subjects for each category below will be tabulated by cohort.

- Any [TEAE](#) and [SAE](#)
- Subjects reporting at least one [TEAE](#) or [TE SAE](#) that is also related to OpRegen
- [TEAE](#) and [SAE](#) Severity: Grade 1/Mild, Grade 2/Moderate, Grade 3/Severe, Grade 4/Life Threatening/Disabling, Grade 5/Fatal
- Categories for all [TEAE](#) and with possible relationship to OpRegen

The following tables will be presented for the number of events by cohort:

- [TEAE](#) by preferred term sorted by descending number of overall events
- [TEAE](#) by SOC, PT\*
- [TEAE](#) by maximum severity\*
- [TEAE](#) by Possible Relationship to OpRegen\*

\*Subjects with >1 [AE](#) in respective category will only be counted once. For maximum severity tabulations, subjects will be counted once in the SOC and PT in the maximum severity.

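### By-cohort TEAE tables show no common observation window, so longer observation of earlier cohorts could hide a rise in TEAEs with dose

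*SAP*

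**What the plan says.** **How TEAEs are summarised.** SAP 7.1.6 says that the overview of TEAEs "with the number of events, number of subjects, and percentage of subjects for each category below will be tabulated by cohort". It then adds: "The following tables will be presented for the number of events by cohort". These further tables cover preferred term, system organ class, maximum severity and relationship to OpRegen. A TEAE is an event that starts, or worsens, at or after administration; the definition shows no upper time limit.

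**How long AEs are collected.** In SAP 7.1.6 the collection period "begins once the subject has signed the informed consent form and ends after the" a point that is blacked out. The protocol is legible. Section 15 states: "All AEs and concomitant medications should be reported over the course of the long-term follow-up period". Section 21.1.6 agrees: "All AEs occurring during the study and long-term follow up period will be recorded and graded".

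**How subjects enter and when data are analysed.** Protocol 6.5 has the targeted doses implanted sequentially with staggered intervals. Protocol 22.14 and SAP 7.0 make each later cohort wait for DSMB review. SAP 9.0 times the short-term analysis from the last subject dosed (interval blacked out) and selects subjects by an assessment that is also blacked out. The legible text gives no per-subject data cut.

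**What the SAP already has.** SAP 4.1.1 defines follow-up time: "Total days on study are the total number of days a subject has been followed up after OpRegen injection". SAP 11.0 lists a Time in Study table (14.1.2), and SAP 7.1.1 reports disposition at the 1 Year Visit. None of these is linked to the AE tables.

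**The concern.** Safety and tolerability are the primary objective, and the incidence and frequency of TEAEs is the first safety endpoint listed (SAP 3.1.1 and 3.2.1). In a dose-escalation study readers will look across the cohort columns for a dose pattern, whether or not a test is planned.

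Sequential entry ties calendar time to cohort. If the tables take everything recorded up to a single calendar cut, Cohort 1 contributes more time per subject than Cohort 4. A crude count or percentage then mixes event rate with observation time. With the longer observation at the lower doses, a real increase with dose is diluted, and can be cancelled or reversed.

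**Working it through.** **Check of the plan's own figure.** The only size figure is 24 treated eyes. Cohort sizes 3 + 3 + 6 + 12 = 24 reproduce it. The documents give no AE rate and no follow-up by cohort, so the rest is illustration under stated assumptions.

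**Inputs**
- Last cohort: 1 year of observation at the short-term analysis. This is assumed; Part 1 lasts about 52 weeks (Protocol synopsis), but the analysis interval is blacked out.
- Early cohort: 62 weeks, 2, 3 or 5 years. The 62 weeks add to 52 the only legible stagger, 6 + 4 = 10 weeks between the first and third subjects of Cohort 1 (Protocol 6.5). It stands in for the between-cohort gaps, which are not legible. The values of 2, 3 and 5 years are assumed.
- Event rate: 0.2 or 2 events per subject-year, assumed, the same in all cohorts and constant over time.

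**Formulas.** With rate r and observation time T, expected events per subject = r × T, and P(at least one TEAE) = 1 − exp(−r × T). The early-to-last ratio of events per subject is T_early / T_last, whatever r is. For 62 weeks it is 62/52 = 1.19.

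| Early cohort, against 1 year in the last | Event ratio, early/last | P(≥1), r = 0.2 (last: 18.1%) | P(≥1), r = 2 (last: 86.5%) | Crude high/low ratio when the true ratio is 2.0 (2.0 / T) |
|---|---|---|---|---|
| 62 weeks | 1.19 | 21.2% | 90.8% | 1.68 |
| 2 years | 2.0 | 33.0% | 98.2% | 1.00 |
| 3 years | 3.0 | 45.1% | 99.8% | 0.67 |
| 5 years | 5.0 | 63.2% | 100.0% | 0.40 |

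For frequent events the percentage saturates, so the event count is affected more than the percentage of subjects.

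**AEs clustered after surgery.** Assume 3 peri-operative events plus 0.5 per year. Events per subject are 3 + 0.5T, against 3.5 at 1 year:
- 62 weeks: 3.6 / 3.5 = 1.03
- 2 years: 4.0 / 3.5 = 1.14
- 3 years: 4.5 / 3.5 = 1.29
- 5 years: 5.5 / 3.5 = 1.57

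**What each remedy does**
- Common window, implantation to 1 year, complete follow-up: equal true rates give a ratio of 1.00 under either pattern, and under the constant rate a true ratio of 2.0 stays 2.0.
- Events per person-year, constant rate: same result.
- Events per person-year, clustered pattern: 3.5 / 1 = 3.5 in the last cohort, against 4.0 / 2 = 2.0 in a cohort with 2 years and 5.5 / 5 = 1.1 in one with 5 years. Identical risk then looks lower in the cohort followed longer.

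**The case against.** The strongest reply is that the case depends on text nobody outside can read. If the blacked-out end of AE collection in SAP 7.1.6, or the blacked-out assessment in SAP 9.0, is a per-subject visit, every completer has the same window and the problem largely disappears. Planned follow-up is not cohort-specific: "Eligible subjects will be enrolled into Part 1 of the trial for approximately 52 weeks", and Part 2 follows for everyone. This stands. A reader might infer that Cohort 1 is in fact followed much longer in these tables; no passage says so.

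Other limits also stand:
- A reader might cite the protocol's mITT set, "which will include all data captured in database for these subjects", as proof that all accrued AEs enter the tables. SAP 6.1 uses the All Treated Population for safety, and that definition has no such phrase.
- The tables are descriptive. SAP 8.0 plans no inference on safety variables unless otherwise specified, and escalation was decided by DSMB review, not by these tables.
- A reader might extend the point to the 5-year analysis. SAP 9.0 selects subjects with a Year 5 assessment, so staggered entry matters there only through events recorded after Year 5. The argument is weak.
- A constant rate is doubtful after a single operation with time-limited tacrolimus. With 3 subjects, a cohort percentage can only be 0, 33, 67 or 100.
- Time in Study is tabulated and AEs are listed by subject, so with 24 subjects a careful reader could reconstruct exposure.

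What the reply does not remove is that the legible SAP nowhere ties the by-cohort tables to a window, while the legible protocol collects AEs well beyond Part 1. A listing lets a reader repair the table; it does not make the table itself interpretable.

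**Conclusion.** The point holds conditionally. If AEs accrued to the short-term data cut are tabulated, earlier cohorts have longer observation, and the crude columns can hide an increase in TEAEs with dose or suggest a decrease. A reader might also infer that follow-up could produce a spurious increase with dose. It cannot in the crude counts, because the extra time falls on the earlier cohorts. That these are the lower-dose cohorts rests on the dosing sequence; each cohort's dose is not legible.

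The inflation in crude events per subject runs from 1.03 to 5.0 across the assumptions above, and a true two-fold increase could appear as anything from 1.68 to 0.40 under a constant rate. The documents do not allow a choice within these ranges. The change is worth making because it is cheap and the tables serve the primary objective. Confidence is low because the deciding text is blacked out.

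**What to change.** In SAP 7.1.6, base the by-cohort TEAE tables on one per-subject window, from implantation to the 1 Year Visit, which SAP 7.1.1 already uses for disposition. Put later events in a separate table, with time in study by cohort beside it. State the window in the table titles in SAP 11.0. If the blacked-out text already sets such a window, confirming it in those titles is enough.

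Add events per person-year, using the total days on study from SAP 4.1.1, only as a supplement. When AEs cluster after surgery, an average rate understates risk in the cohorts followed longer, so the common window should lead.

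The cost is one window flag, one extra table and one rate column. SAP 2.0 allows revisions before database lock, with reasons given in the study report. The change does not make the cohorts otherwise comparable: Cohort 4 also differs in BCVA, formulation and delivery device, and subjects who leave before the 1 Year Visit still contribute less time.

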Cohort 4 will include two formulations; subjects will be treated with either OpRegen® BSS Plus or OpRegen® ‘Thaw-and-Inject’ (TAI) formulation, which is based on the use of CryoStor® 5, a serum-free, animal-free GMP grade cryopreservation solution. Additionally, this Cohort includes two options for subretinal delivery systems: DORC² or the Orbit SDS (an FDA 510K class II device cleared under K182274 on 20 November 2018). Please refer to the instructions for use (IFU) for each device for more information.

Staggered intervals will be applied between at least the first two subjects of each delivery modality to ensure subject safety and welfare.

[REDACTED]

[REDACTED]

All Cohorts

The study is being conducted in participants with confirmed bilateral GA (Study Eye and Non-Study, Fellow Eye).

Between cohorts and subjects, where applicable, the next step to proceed will be per Data Safety Monitoring Board (DSMB) recommendation, based on accumulated safety data.

Cell suspension will be delivered into the subretinal space in the macular area as described in the IFU and operating manuals for each delivery device.

[REDACTED]

[REDACTED]

[REDACTED]

[REDACTED]

[REDACTED]

Along with the relevant surgical procedure, subjects will receive systemic immunosuppression [REDACTED], consisting of the following:

- [REDACTED]
- Systemic (PO) tacrolimus 0.01 mg/kg daily [REDACTED] up to 6 weeks post transplantation,
- Systemic (PO) mycophenolate mofetil, up to 2 gr/day, [REDACTED] for at least three months [REDACTED] post transplantation, [REDACTED]

During Part 1 of the study, subjects will be assessed at pre-scheduled intervals throughout the [REDACTED] following the implantation of OpRegen®. Any side effects related to the immunosuppressive treatment will be monitored and followed up (e.g. improve blood pressure control if hypertension develops). In the case of uncontrollable side effects, treatment with the immunosuppressive agents described above will be modified in consultation with the Medical Monitor.

Part 2 of the study includes long term follow-up visits that will occur at [REDACTED]

Study Population and Number of Subjects

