8.1.1 Number of Subjects

Approximately 24 subjects will be enrolled in four cohorts, with three subjects enrolled in each of the first two cohorts, up to 6 subjects in the third cohort, and approximately 12 subjects enrolled in the fourth cohort.

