22.10 EVALUATION OF SAFETY

22.10.1 Treatment Emergent Adverse Events (TEAEs)

AEs will be recorded from the time a subject has signed the Informed Consent. All AEs reported by the investigators will be coded according to the current version of the MedDRA dictionary.

The following will be incorporated into the analysis of AEs:

- All analyses to be provided will include coded AEs.
- AEs analyses will include only the TEAEs, namely, those events which started following study IP implantation. Listings of both TEAEs and non-TEAEs will be provided.
- Summary tables of TEAEs will be provided by Study Cohort and overall.
- The incidence (no. of subjects) and frequency (no. of events) of TEAEs will be provided when broken down by System Organ Class (SOC) and by Preferred Term (PT) according to MedDRA dictionary.
- Breakdowns of TEAEs by all of the AEs attributes (e.g. seriousness, severity) will also be provided.
- Breakdowns of TEAEs by age and sex will also be provided.
- The derived dictionary used in the analyses displaying the MedDRA System Organ Class (SOC), the Preferred Term (PT), and the AE Verbatim Term as specified by the Investigator, will be provided.

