## 2.0 INTRODUCTION

### General Overview

CCN\_CT02 is a Phase I/IIa, multicenter, multinational open-label, interventional clinical trial of OpRegen®, a cell-based product composed of retinal pigment epithelium ([RPE](#)) cells, derived from human embryonic stem cells ([hESCs](#)) through a process of directed differentiation, which are implanted as a single administration to the worst vision eye of patients with advanced dry-form age-related macular degeneration ([AMD](#)) and geographic atrophy ([GA](#)) as a cell suspension ([www.ClinicalTrials.gov](http://www.ClinicalTrials.gov) Identifier: NCT02286089). The study involves dose escalation cohorts of targeted suspensions of  $50 \times 10^3$  to  $200 \times 10^3$  cells [REDACTED]

[REDACTED]  Two methods of subretinal surgical administration of OpRegen were employed during the study; 1) pars planar vitrectomy (PPV) and retinotomy or, 2) [REDACTED], which utilized a sclerotomy and [REDACTED] route to access the subretinal space.

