#### 4.0 STUDY DESIGN

Open-label, dose escalation study of 24 subjects with advanced dry-[AMD](#) and [GA](#) divided into four cohorts ([Figure 1](#)):

##### Cohorts 1 – 3

The first 2 cohorts, consisted of 3 eyes of 3 legally blind subjects with best corrected visual acuity of 20/200 or less in the study eye, all received a single subretinal implantation of OpRegen.

The third cohort included 6 eyes of 6 subjects with best corrected visual acuity of 20/200 or less in the study eye, all received a single subretinal implantation of OpRegen.

Staggered intervals and safety data review by the independent data safety monitoring board ([DSMB](#)) occurred within and between cohorts to ensure subjects safety and welfare.

##### Cohort 4

The fourth cohort included 12 eyes from 12 subjects with [BCVA](#) between 20/64 and 20/250 in the study eye, all received a single subretinal targeted implantation of OpRegen.

Staggered intervals and safety data review by the [DSMB](#) occurred between at least the first two subjects of each delivery modality to ensure subject safety and welfare.

[figure not shown]

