## 8.0 GENERAL CONSIDERATIONS

In general, numerical variables in demographic and baseline characteristics will be summarized by displaying: n (non-missing sample size), mean, standard deviation, median, quartiles, maximum and minimum. The frequency and percentages (based on the non-missing sample size) of observed

levels will be reported for all categorical measures. Percentages will be calculated out of the total number of subjects per group.

Numerical effectiveness variables described above will be summarized displaying n, mean, median, standard deviation ([SD](#)), standard error (SE), quartiles, minimum, maximum.

All summary tables will be structured with a column for either treated or fellow eye.

No inferential statistics will be applied to baseline characteristics and safety variables unless specified otherwise.

In general, all data will be listed and sorted by treatment or fellow eye status, cohort number, site and subject, and when appropriate by visit number (or assessment date) as appropriate.

Most data manipulation, tables, figures, listings, and analysis will be documented in SAS programs and performed using SAS® Software version 9.4.

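### Cohort 4 mixes two formulations and two delivery systems, but adverse events are tabulated by cohort with no split by either, and no planned table reports the device events of special interest

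*SAP*

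**What the plan says.** **Composition of Cohort 4.** The protocol synopsis says "Cohort 4 will include two formulations" (BSS Plus or Thaw-and-Inject) and "Additionally, this Cohort includes two options for subretinal delivery systems" (DORC or the Orbit SDS). SAP 2.0 confirms the second point in the past tense: "Two methods of subretinal surgical administration of OpRegen were employed during the study". On size, SAP 4.0 says "The fourth cohort included 12 eyes from 12 subjects".

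**Delivery as a risk in its own right.** The synopsis and SAP 4.0 stagger at least the first two subjects of each delivery modality, and SAP 4.0 adds DSMB review. Protocol 6.6.1 links lens clouding and possible cell egress to vitrectomy and retinotomy. Protocol 21.2, Table 8, grades device events of special interest, including retinal perforation, cell egress, failure to deliver cells and unplanned vitrectomy.

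**Reporting.** In SAP 7.1.6 the topline TEAE summary "for each category below will be tabulated by cohort", and the further TEAE tables are also by cohort. Protocol 22.10.1 says "Summary tables of TEAEs will be provided by Study Cohort and overall", with breakdowns by AE attributes, age and sex. SAP 6.4 speaks of dose regimen groups and overall. Listings are in general "sorted by treatment or fellow eye status, cohort number, site and subject" (SAP 8.0). Section 11 has TEAE tables by system organ class and preferred term, seriousness, relationship to per-protocol treatment, ocular toxicity and systemic toxicity. None has a title naming formulation, delivery system or Table 8.

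**The concern.** Safety and tolerability is the primary objective, and Cohort 4 is half of the trial. During conduct the documents treat the delivery routes as different exposures. In the planned tables that distinction disappears. If an event clusters under one delivery system or one formulation, the tables show a single Cohort 4 rate: too low for the affected group and too high for the other. Nothing in the table tells the reader that the rate is a mixture.

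The device events are a related gap. Table 8 sets up a graded scale for events tied to delivery, but the SAP plans no table for it. The relatedness summaries that can be read address OpRegen and the per-protocol medications, not the device or the procedure.

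**Working it through.** **Inputs**

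| Input | Value | Source |
|---|---|---|
| Cohort sizes | 3, 3, 6, 12 | SAP 4.0; Protocol 8.1.1 plans up to 6 in Cohort 3 and "approximately 12 subjects enrolled in the fourth cohort" |
| Formulations in Cohort 4 | 2 | Protocol synopsis |
| Delivery systems in Cohort 4 | 2 | Protocol synopsis; SAP 2.0 |
| Split of Cohort 4 | not readable | Protocol 10 names a group of 6, but its descriptor is redacted |
| MTD rule | at least two subjects with a DLT in a cohort | Protocol 22.14; SAP 7.0 |

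The split is an assumption: 6/6 as the base case, with a range of 3/9 to 9/3. All event rates below are illustrative.

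**Step 1. The plan's own total.** 3 + 3 + 6 + 12 = 24, as stated.

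**Step 2. How far pooling moves a rate.** If k of the 12 subjects have true rate p and the rest have rate q, the tabulated rate is [k·p + (12 − k)·q] / 12. With q = 0 this is (k/12)·p:

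- k = 3: one quarter of the affected group's rate
- k = 6: one half
- k = 9: three quarters

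**Step 3. Illustration with exact (Clopper-Pearson) 95% intervals.**

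| Assumed split | Affected group | Other group | Planned table |
|---|---|---|---|
| 6/6 | 3/6 = 50.0% (11.8 to 88.2) | 0/6 = 0% (0 to 45.9) | 3/12 = 25.0% (5.5 to 57.2) |
| 3/9 | 3/3 = 100% (29.2 to 100) | 0/9 = 0% (0 to 33.6) | 3/12 = 25.0% (5.5 to 57.2) |

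The upper limit for 0/9 is 1 − 0.025^(1/9) = 0.336. Two very different patterns give the same planned entry.

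**Step 4. Does pooling also weaken the DLT count?** The rule is a number of subjects, not a proportion. In a group of 6 with DLT rate p, P(at least 2) = 1 − (1 − p)^6 − 6p(1 − p)^5. At p = 0.30 this is 1 − 0.118 − 0.303 = 0.580.

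- Other six at rate 0: the pooled cohort gives the same 0.580.
- Other six at rate 0.05: P(0) = 0.1176 × 0.7351 = 0.0865. P(1) = 0.3025 × 0.7351 + 0.1176 × 0.2321 = 0.2497. So P(at least 2) = 0.664.

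Pooling cannot lower the chance of meeting the rule; it can only leave it equal or raise it.

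**Step 5. What a split could show.** For 3/6 against 0/6 the two-sided Fisher p-value is 2 × C(6,3)/C(12,3) = 40/220 = 0.18. The intervals in Step 3 overlap widely. Split tables would describe; they could not establish a difference.

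**The case against.** The best reply is that little information is lost. SAP 7.1.6 lists every AE by subject, SAP 7.0 promises listings of all eCRF information and derived variables, and Section 11 plans a surgical procedure table (14.1.5) and listing (16.1.5). With 12 subjects, a reader could probably match events to delivery method. The DSMB also reviewed the first subjects of each modality. The study is unpowered and descriptive, and the split cells would be small. All of this is correct, and it keeps the point modest. It does not remove it. Hand-matching across listings is no substitute for a summary on the primary objective, DSMB review protects conduct rather than reporting, and the plan already reports cohorts of 3.

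Redaction is a fair limit too. Text after the Cohort 4 description, the opening of Protocol 21.2 and the unshown Figure 1 may define sub-cohorts. The readable wording of SAP 7.1.6 and the readable Section 11 titles do not use any.

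A reader might infer more than the documents support:

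- *That the DLT/MTD count is diluted.* It is not (Step 4). What pooling loses there is attribution, since one DLT in each group would also meet the rule. The MTD text gates the moves to Cohorts 2 and 3; Cohort 4 opens on DSMB review.
- *That Cohort 4 holds four crossed treatment packages.* Nothing readable says that formulation and delivery were crossed.
- *That a Cohort 3 to Cohort 4 difference will be read as a dose effect.* No such safety comparison is planned in the readable text, and the dose assigned to each of these cohorts cannot be read.
- *That the choice of formulation and delivery for the next study depends on this split.* The protocol speaks only generally of informing future trials.

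**Conclusion.** The point holds as a gap in reporting. As planned, a TEAE specific to one formulation or delivery system appears in the tables only within a pooled Cohort 4 rate (and, under the protocol, an overall rate), and the Table 8 device events have no table. With no background events, the tabulated rate is one quarter to three quarters of the affected group's rate as that group runs from 3 to 9 of the 12 subjects, and one half under a 6/6 split. The direction does not depend on the split; the size does, and both the split and the event rates are assumed.

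It does not follow that subject-level information is missing or that any stopping or escalation rule is weakened. This is a cheap improvement, held with moderate confidence because of the redactions.

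**What to change.** In SAP 7.1.6 and Section 11:

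1. For Cohort 4, add descriptive tables of TEAEs, SAEs and ocular toxicity as x/n by delivery system and, separately, by formulation, beside the cohort total.
2. Add one table of the Protocol Table 8 device events of special interest by delivery system.
3. Add delivery system and formulation as columns in the AE listings.

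This point gives no reason to alter the DLT/MTD count.

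**Cost:** a few extra tables. The trial must know which product and device each treated subject received. A surgical procedure listing is already planned, and Protocol 17 keeps batch and chain-of-custody papers with the trial or subject records. No readable text confirms an eCRF field for formulation, so it may have to be derived from those records. The downside is small denominators: even 0/6 is compatible with a rate of up to 45.9%. The tables should be labelled descriptive, without between-group tests.
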